# Methodology

# **Research Design**

This study is a single-center, investigator-designed and led clinical trial testing the efficacy of the breath ketone analyzer, Biosense, for the detection of ketogenesis during four distinct study periods, which will allow comparisons of the Biosense measured breath ketones with capillary BOHB and both of these point of care (POC) tests with laboratory measured BOHB and acetoacetate (AcAc). Ethics approval will be from the Washington University Human Studies Protection Office, and obtained prior to contact with any potential participant. Participants with T1D using a stable form of insulin delivery, either insulin pump or multiple daily injections (MDI) and will perform paired measurements of capillary BOHB and BrACE during usual care or usual care plus therapy with a SGLT2i. Paired testing will then be done during insulin withdrawal in usual care and insulin withdrawal while taking a SGLT2i that has reached steady state.

Participants will be randomized to Group A, in which the usual care segment and insulin withdrawal day is done first followed by the usual care plus SGLT2i and insulin withdrawal with SGLT2i or Group B, in which the SGLT2i will be taken during usual care for 2 weeks, then insulin withdrawal with SGLT2i followed by usual care for 2 weeks then insulin withdrawal during usual care. The study design is robust, and will allow more than 800 paired measurements of breath ketones with capillary BOHB during usual care, more than 800 paired measurements during usual care plus SGLT2i therapy. Additionally, due to concerns about ketogenesis during times of insulin deficiency, and the demonstrated increase in ketone generation with SGLT2i therapy, the pair-wise comparisons will be informative about the correlation of BrACE as measured with the Biosense device with POC and laboratory BOHB measurements and laboratory measured AcAc.

Dapagliflozin, 10 mg was selected over the other FDA approved SGLT2i drugs because this dose was used in the recently published study, DAPA-CKD, which showed remarkable reduction in progression of

kidney function decline in persons with and without T2D, HR 0.61 (95% CI, 0.51 - 0.72). Reduction in the progression of diabetic kidney disease is a high priority for persons with T1D. In the study procedures, SGLT2i refers to dapagliflozin, 10 mg daily.

Research subjects will be persons with T1D who are using continuous glucose monitoring (CGM) with Dexcom G6 and either an insulin pump or multiple daily injections (MDI) with long-acting insulin (insulin glargine U100) administered in the morning. Recruitment will take place from our Washington University-Barnes Jewish Hospital Diabetes Center, which cares for over 1200 persons with T1D per year. Availability of medical records is considered key to appropriate patient selection and follow-up of any adverse events, thus persons outside of our system will not be recruited for the study. Participants must be able to use a smart phone with applications for their CGM device, insulin pump (if using) and the Biosense BKA device. The inclusion and exclusion criteria are listed below. Every effort will be made to recruit participants across the age range of the study, and to include persons of both genders and of different races and ethnicity, based on our local population.

Inclusion criteria:

- Type 1 diabetes for >1 year
- Age 18 75, any gender, race or ethnicity
- HbA1c <10%
- Stable insulin delivery method for the past 30 days
- Vision of 20/40 or better, including ability to read all device instructions and insulin pump settings
- Use of an insulin pump and ability to make adjustments to pump settings
- Insulin delivery by MDI with basal insulin (glargine U100) given in the morning OR willingness to transition to basal glargine given in the morning for at least 48 hours prior to insulin withdrawal visits
- Use of personal CGM, only Dexcom G6 will be permitted for data consistency
- Use of cellular phone (iOS11 and above or Android) with data capability with connectivity to Dexcom Clarity app and Biosense Ketone Monitoring app
- Willing to share CGM, capillary ketone results and BrACE data with the study group
- Able to understand the study requirements, risks and benefits and able to provide written informed consent
- Able to schedule the visits and perform study related tasks

Exclusion criteria:

- History of DKA in the past 6 months, or more than 1 episode of DKA in the past 2 years
- Use of insulin degludec, insulin glargine U300 or insulin detemir as basal insulin and unwilling to transition to glargine given in the morning for at least 48 hours before the insulin withdrawal visits
- Use of an SGLT2i in the past 30 days or intolerance to SGLT2i use in the past for any reason
- Unstable heart disease, including hospitalization for any cardiac or vascular event in the past 6 months.
- eGFR <30 ml/min/1.73m2 or hemoglobin <11.0 g/dL measured in the past year
- Cancer that has been under treatment in the past 6 months, or treatment is likely in the 3 months after signing the consent, not including skin cancer or cancers under long-term hormonal reduction treatment (breast or prostate, no other active treatment)
- Psychiatric condition that interferes with daily activities or diabetes self-care, including substance abuse
- Any illness or condition that may interfere with study measurements, or contraindications for use of SGLT2i, based on investigator discretion (hemoglobinopathy, orthostatic hypotension)
- Unwilling to avoid alcohol during the active study periods, specifically to avoid alcohol for 4 hours prior to any breath ketone measurement

- Currently following or planning to adopt a diet that is low in carbohydrates (defined as <90 grams of carbohydrate per day) or is expected to be ketogenic
- Use of oral or injected corticosteroids within the past 30 days or planned during the study period
- Taking disulfiram (due to interference with breath ketone measurements)
- History of vomiting episodes for any reason in the past 30 days, or hospitalization for cyclic vomiting in the past year
- History of urinary tract infection in the past 3 months
- Pregnancy, breast-feeding or intention of becoming pregnant during the study time period and up to 30 days after study completion
- Pre-menopausal women not using acceptable birth control defined as abstinence, surgical sterilization, hysterectomy, hormonal contraception, IUD or proven effective barrier methods

The five study data-collection periods are as follows:

- 1. Visit 1 will collect demographic, medical history, insulin administration and insulin dose data; CGM download, lab draw if needed, and training on capillary ketone measurements using the Precision Xtra meter and breath acetone using the Biosense breath ketone analyzer. Dapagliflozin tablets will be provided to participants randomized to Group B. Recommendations for change in insulin regimen or insulin doses will be made at this visit.
- Segment 1 will consist of 2 weeks of usual care with participants measuring fasting and random breath ketones paired with capillary BOHB (Group A) or usual care plus dapagliflozin with participants measuring fasting and random breath ketones paired with Capillary BOHB (Group B). Participants will be instructed to do paired ketone testing anytime their glucose is >250 mg/dL, or if they develop symptoms of feeling unwell for any reason.
- 3. Visit 2 will be a single day of on-site close monitoring during insulin withdrawal. Morning insulin doses will be withheld, and the participants will have hourly checks of glucose, capillary BOHB, breath ketones, blood BOHB and acetoacetate. CBC will be done at baseline, and BMP to check electrolytes will be done at baseline and every 2 hours until the study end. Instructions for Segment 2 will be provided and recommendations for change in insulin regimen or insulin doses will be made at this visit.
- 4. Segment 2 will consist of 2 weeks of usual care (Group B) or usual care plus therapy with dapagliflozin SGLT2i (Group A). Participants will be instructed to do paired ketone testing fasting and randomly during the day, and if their CGM glucose exceeds 250 mg/dl or if they feel unwell.
- 5. Visit 3 will be a single day of on-site close monitoring during insulin withdrawal (Group B), but after taking an SGLT2i tablet (Group A). Morning insulin doses will be withheld, and the participants will have hourly checks of glucose, capillary BOHB, breath ketones, blood BOHB and acetoacetate. CBC will be done at baseline, and BMP to check electrolytes will be done at baseline and every 2 hours until the study end.

The study design and schematics are depicted below:

	Phone								Visit 3 /FOS
GROUP A	or clinic visit	Visit 1	Gap d	Usual Care + Ketone Monitoring	Visit 2 IRU Insulin Withdrawal	Gap e	Optional Visit	Usual Care + SGLT2i + Ketone Monitoring	IRU Insulin Withdrawal
		On-site		HOME- Segment 1 14 +/-2 days	On-site		Phone or on-site	HOME - Segment 2 14 consecutive	On-site
Phone screening	х								
Informed Consent discussion	Х	Х							
Informed Consent	X	X							
Demographics, medical, medication and		v							
Vital signs, height, weight		×							
Inclusion/exclusion review	x	x							
Physician H&P	~	X							
Near Vision Accuity Screening		x							
CGM check for connectivity to clinic		X							
Dispense capillary ketone meter and									
supplies, breath ketone analyzer		X							
Training on the capillary ketone meter		Х							
Training on the breath ketone analyzer,		v							
ensure app download and connectivity		^							
Training on the study requirements, diary		Х							
Randomization		Х							
CGM download	Х				X		Х		Х
Ketone testing 3X daily, capillary and breath				Х				X	
								va	
Vital signs of hours and pro					x			~	x
Urine Pregnancy test as needed		x			x		х		x
HbA1c		X					~		
BMP and CBC b		Xp							
CBC, BMP, BOHB, AcAc c baseline					х				Х
BMP q 2 hours					х				Х
Laboratory BOHB , AcAc c g 1-2 hours					х				Х
Future research stored blood samples					х				Х
Capillary BOHB q 1 hour					х				Х
Capillary glucose q 1 hour					х				Х
Breath ketone measurement q 1 hour					х				Х
Urine sample for ketones					х				Х
Standard meal at the end					X				Х
Physician oversight, MDI user if basal insulin adjustment required		x							
Physician oversight, safety assessment, correction insulin dose +/- fluids administered					х				x
Dispense SGLT2i tablets					х				
Adverse events and concomitant medication review		х			x		х		х
Return and count SGLT2i tablets									Х
Ketone Use Survey f					Х				Х
a. Home pregnancy test for WOCBP before star	ting SGL	F2i if 4 we	eks or mor	e since on-sit	te Visit 2				
b. If lab results within 12 months prior to scree	ning are	not availa	ble						
c. May be performed									
d. May be Gap between Visit 1 & Start of Usual	care seg	ment of u	p to 2-3 we	eeks					
e. May be Gap between Visit 2 & start of SGLT2	segmen	nt of up to	2-3 weeks	if scheduling	sissues arise. S	ubject should	NOT start da	pagliflozin sooner	than 14
days before Visit 3. Subject must have taken da	apagliflo	zin for 14	consecutiv	ve days prior t	to the day of Vis	sit 3.			
f. Survey may be provided on paper or electron	ically								

GROUP B	Phone or clinic visit	Visit 1	Optional Visit	Gap d	Usual Care + SGLT2i + Ketone Monitoring	Visit 2 IRU Insulin Withdrawal	Gap e	Usual Care + Ketone Monitoring	Visit 3/EOS IRU Insulin Withdrawal
		On-site	Phone or on-site		HOME - 14 consecutive days	on-site		HOME - 14 +/-2 days	On-site
Phone screening	Х								
Informed Consent discussion	Х	Х							
Informed Consent	Х	Х							
Demographics, medical, medication and									
device use history		X							
Vital signs, height, weight		X							
Inclusion/exclusion review	X	X							
Physician H&P		X							
Near Vision Acculty Screening		X							
CGIVI check for connectivity to clinic		X							
supplies breath ketene analyzer		х							
Training on the capillany kotone motor		v							+
Training on the breath ketone analyzer		^							
ensure and download and connectivity		Х							
Training on the study requirements diany		x							
Randomization		X							
CGM download	х	~	х			х			x
Ketone testing 3X daily, capillary and breath	~		~		х	~~~~~~~~~~~~~~~~~~~~~~~~~~~~~~~~~~~~~~~		x	
					~			~	
Home Pregnancy test WOCBP a					x a				
Vital signs of hours and prn					~	х			x
Urine Pregnancy test as needed		х	х			X			X
HbA1c		X							
BMP and CBC b		xb							
CPC PMP POHP AcAc c baseline		Λ				x			×
RMP a 2 hours						×			×
						^ V			×
Laboratory BOHB , ACAC q 1-2 hours						^ V			^ 
Future research stored blood samples						X			X
Capillary BOHB q 1 hour						X			X
Capillary glucose q 1 nour						X			X
Breath ketone measurement q 1 nour						X			X
Standard moal at the end						X			×
						^			
Physician oversight, MDI user if basal insulin adjustment required		x							
Physician oversight, safety assessment		1							
correction insulin dose +/- fluids administered						X			X
Dispense SGLT2i tablets		х							
Adverse events and concomitant medication									
review		х	Х			Х			X
Return and count SGLT2i tablets		1				Х			
Ketone Use Survey f					Х				х
a. Home pregnancy test for WOCBP before start	ting SGLT	2i if 4 we	eks or more	since on-si	te visit 1	ı			-
b. If lab results within 12 months prior to screer	ning are i	not availa	ble						
c. May be performed									
d. May be Gap between Visit 2 and start of SGLT2i segment of up to 2-3 weeks if scheduling issues arise. Subject should NOT start dapagliflozin sooner than 14									
days before Visit 2. Subject must have taken dapagliflozin for 14 consecutive days prior to the day of Visit 2.									
e. May be Gap between Visit 2 & usual care of u	ip to 2-3	weeks							
f. Survey may be provided on paper or electron	ically								

# Figure 2: Study visits

The study visits will include the following activities and measurements:

# PRESCREENING

The prescreening visit may be conducted by phone after the clinic chart of the potential participant has been reviewed and a discussion with the treating endocrinologist has taken place. The prescreening study staff will explain the study purpose, study activities, study expectations and the risks and benefits of participation. The informed consent will sent via email with the patient's permission to use email communication. A second discussion may take place by phone or in person at the screening visit to answer questions about information provided in the informed consent document, study procedures and risks and benefits.

# VISIT 1

This visit will take place on-site in the Diabetes Center. After all questions have been answered and the patient provides written informed consent, which will be co-signed by an investigator, study activities will commence. Health information collected will include basic demographics, history of diabetes onset, current therapy, episodes of severe hypoglycemia or DKA and diabetes complications. Medications will be reviewed and recorded, including mean insulin doses over the past 3 days. If participant is on MDI therapy taking basal insulin in the evening and/or uses other than glargine as basal insulin, study physician will adjust delivery time to morning and/or make changes to basal insulin glargine for at minimum 48 hours prior to visits 2 and 3. History of alcohol use, smoking (including marijuana) and any CNS depressants (sleeping pills, pain medications) will be reviewed, and may be a cause for investigator recommended non-participation if paired testing cannot be completed without interferences. Women with child-bearing potential must be using acceptable birth control (barrier, hormonal, IUD, confirmed abstinence or surgical) during the study and must consent to pregnancy testing at specified intervals. Breast-feeding is a cause for exclusion from the study. Vital signs, height, weight and HbA1c will be obtained. An optional BMP and/or CBC may be done if evaluation of kidney function or red blood cell count is determined to be important to meet eligibility criteria. All data will be entered into a dedicated Redcap database.

After the investigator or sub-investigator determines that the participant meets all of the inclusion and none of the exclusion criteria, the study team will proceed with interrogation of the participant's CGM to ensure appropriate connectivity with the study team. Participants will be asked to demonstrate competency in making changes to insulin pump settings. The study team members will train the participant in the use of the Precision Xtra ketone meter and the Biosense BKA. Participants will be instructed to wait 60 minutes after eating, smoking/vaping, drinking sodas or flavored waters or consuming items such as toothpaste, mouthwash, cough drops, breath mints, chewing gum, lip balm and artificial sweeteners before doing a BrACE measurement. If using alcohol, participants should wait 4 hours before testing with the BKA. Participants will be instructed in avoidance of environmental contaminants also. Participants will be able to test capillary BOHB even when conditions are not optimal for BrACE.

The participant will upload the Biosense app onto his or her smart phone and test a test run will be conducted. A diary will be provided for entry of BOHB ketone measurements and BrAce with space for comments in case of known interference with BrAce or other problems with measurements. A written ketone action plan will be provided to all participants in the study. Participants will be informed that they may stop participating in the study at any time without loss of usual care of their diabetes.

A ketone action plan will be provided to each participant that will include the following elements: ingestion of carbohydrates, fluid intake and insulin administration with doses of insulin adjusted according to individual requirements. Participants will be asked to employ the ketone action plan if BOHB reading is >1.5 mmol/L. BrACE levels of >15 in the absence of corresponding BOHB level >1.5 mmol will be considered due to contamination and the participant will be asked to repeat the levels in 1 - 2 hours.

Patients will be randomized by card draw in lots of 4 to Group A or Group B

**USUAL CARE** (Group A will do this first, Group B will do this segment after the SGLT2i) The participant will manage his or her diabetes in the usual way, with no effort to modulate glucose levels for the study. Participants will check breath ketones with the Biosense BKA and capillary BOHB with the Precision Xtra ketone meter when fasting and at one or two other times during the day, plus any optional measurements. See instructions above for avoidance of biologic or environmental contaminants. There is no mandated contact with the participant, but participants can contact the study team at any time for questions, to report device issues or discuss glucose or ketone levels.

#### On-site Visit

The on-site will be conducted at the Intensive Research Unit at Washington University. Patients will be asked to arrive fasting, to stop their basal insulin delivery 1 hour before arrival at the center if on an insulin pump or to hold injectable insulin doses. Prior to leaving home, the participant's blood glucose should be 90 – 250 mg/dL, and BOHB <1.5 mmol/L, or the test day will be rescheduled. Time of the last insulin dose will be recorded. Vital signs and baseline labs including a CBC, BMP and pregnancy test in women with child-bearing potential will be done. Measurements of capillary BOHB using the Precision Xtra meter and BrACE using the Biosense BKA will be done hourly X7 or 8 if the patient remains relatively asymptomatic, and the capillary BOHB level does not exceed 4 mmol/L. If the capillary BOHB reaches 2.5 mmol/L or capillary glucose reaches 250 mg/dL, the capillary finger sticks and breath measurements may be collected at 30 minute intervals. The venous blood samples will continue to be collected on the hour intervals. Venous blood samples for BMP, BOHB and AcAc\* will be drawn at baseline and every 2 hours X3 plus the end of the study.

The insulin withdrawal portion of the study will end (stopping rules) upon patient request for any reason, if the patient becomes symptomatic with nausea or vomiting (even if he or she does not request that the study be stopped), after 7 hours of fasting without insulin, or if either the capillary BOHB is  $\geq$ 4 mmol/L or the CGM blood glucose is  $\geq$ 400 mg/dL. BMP will be done every 2 hours and at the end of the study. At the termination of the ketogenic fast, participants will be given a correction dose of rapid acting insulin subcutaneously or regular insulin IV, per investigator discretion. They will then restart insulin via insulin pump, or administer both basal and mealtime insulin via subcutaneous injection and be given a standard meal. Participants will be observed for a minimum of 1 hour after the study end for return to near normal metabolic status. An additional contact by phone or other means in the evening will be made to confirm safety and no adverse consequences of the study day.

At the end of this visit, the next part of the study will be scheduled. The participant will be provided with dapagliflozin, 10 mg, 14 tablets. The participant will be asked to take the pills daily for 14 days prior to Visit 3 which is conducted on-site. If a gap in scheduling occurs such that visits 2 and 3 are more than 4 weeks apart, women of child-bearing potential will be asked to complete a home pregnancy test, with photographic proof that it is negative before starting dapagliflozin.

The ketone action plan will be discussed again with each participant. Elements of the plan will during PERIOD 2 will include: stopping the SGLT2i medication, ingestion of carbohydrates, fluid intake and insulin administration with doses of insulin adjusted according to individual requirements. Participants will be asked to employ the ketone action plan if BOHB reading is >1.5 mmol/L. BrACE levels of >15 in the absence of corresponding BOHB level >1.5 mmol will be considered due to contamination and the participant will be asked to repeat the levels in 1 - 2 hours. Participants will be given numbers of study personnel to call for ongoing advice about management of ketosis.

**USUAL CARE + SGLT2i (**Group B will do this segment first, followed by usual care without SGLT2i) The participant will commence taking dapagliflozin, 10 mg daily, for 14 days before Visit 3. Insulin doses will be reduced by 10% basal and 15% bolus. Insulin dose adjustments will be determined by an investigator at the end of Visit 2. Participants will check BrACE with the Biosense BKA and capillary BOHB with the Precision Xtra ketone test strips when fasting and at two other times during the day. Each time point should be at least 4 hours after ingesting alcohol. Participants will be instructed in avoidance of contamination with other alcohol sources such as swabs, nail polish remover, hand sanitizer and other

solvents during the testing period. The study team will remotely monitor the participant's glucose within a few days of starting the SGLT2i and again prior to the on-site visit to ensure safety. There is no mandated contact with the participant, but participants can contact the study team at any time for questions.

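### Minor safety-procedure inconsistency: in Group A the text and the schedule table set different triggers for the home pregnancy test before dapagliflozin, and they disagree at permitted gaps of 15 to 21 days

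*Combined protocol and SAP*

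**What the plan says.** All references are to the combined protocol and SAP.

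- **On-site Visit, Group A order.** Tablets are handed out at the end of Visit 2: "The participant will be provided with dapagliflozin, 10 mg, 14 tablets". Dosing is tied to the next visit: "The participant will be asked to take the pills daily for 14 days prior to Visit 3 which is conducted on-site". The same section makes a home pregnancy test conditional on timing, and the condition reads "If a gap in scheduling occurs such that visits 2 and 3 are more than 4 weeks apart". When it is met, those who could become pregnant must send a photograph of a negative result ahead of the first dose.
- **Figure 2, Group A schedule, footnote a.** It begins "Home pregnancy test for WOCBP before star" (the word is cut by text extraction). It makes the test conditional on 4 weeks or more since on-site Visit 2.
- **Figure 2, Group A schedule, footnote e.** It begins "May be Gap between Visit 2 & start of SGLT2" and allows that gap to run up to 2-3 weeks when scheduling is difficult. It also bars starting the drug earlier than 14 days before Visit 3 and requires 14 consecutive days of dosing first.
- **Figure 2, Group B schedule.** Footnote a uses the same 4-week trigger, counted from Visit 1. No body text gives Group B a different trigger. Footnote d describes the gap before the SGLT2i segment as starting at Visit 2, although in Group B that segment comes before Visit 2.
- **Visit 1.** Women of child-bearing potential "must consent to pregnancy testing at specified intervals".

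**The concern.** The same test, in the same women and for the same purpose, has two triggers in current text, and their clocks stop at different events. The body text counts from Visit 2 to Visit 3. The footnote counts from Visit 2 to the first dose, which comes 14 days earlier. Both use 4 weeks, so the two rules look alike and the mismatch is easy to miss.

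Pregnancy is an exclusion, and participants consent to testing at intervals that the protocol is supposed to specify. In Group A the drug goes home at Visit 2 and is started there, with no mandated contact before the first dose. The home test is the only conditionally required check between the Visit 2 test and the start of dosing. The next required test is at Visit 3, after 14 home doses. Whether a woman with a third-week gap is retested therefore depends on whether staff follow the text or the table.

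**Working it through.** The plan gives no figure to reproduce. The check is a day count.

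**Inputs**

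- Let *g* be the days from Visit 2 to the first dapagliflozin dose.
- Visit 3 falls on day *g* + 14 (On-site Visit; footnote e).
- Permitted *g*: up to 2-3 weeks, so at most 21 days at the upper end and 14 at the lower (footnote e).

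**Triggers in terms of *g***

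- Body text: Visit 2 to Visit 3 exceeds 28 days, so *g* + 14 > 28, which gives *g* ≥ 15.
- Footnote a: *g* ≥ 28, which puts Visit 3 at day 28 + 14 = 42 or later.

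| Gap *g* (days) | Visit 2 to Visit 3 (days) | Body text | Footnote a | Within permitted gap? |
|---|---|---|---|---|
| 0-14 | 14-28 | no test | no test | yes |
| 15-21 | 29-35 | test | no test | yes |
| 22-27 | 36-41 | test | no test | no |
| 28 or more | 42 or more | test | test | no |

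**Size of the difference within the permitted gap**

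- Oldest Visit 2 result at first dose without a retest: 14 days under the text, 21 under the footnote, a difference of 7 days.
- Longest interval between the Visit 2 and Visit 3 tests without a home test: 14 + 14 = 28 days under the text, 21 + 14 = 35 under the footnote.

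**Sensitivity to the reading**

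- If *g* counts full days between, so that dosing starts on day *g* + 1, the text applies from *g* = 14 and the footnote from *g* = 27. The disagreement within the permitted gap is then 14-21 days.
- If the gap is held to 14 days, the rules do not differ on the main count. On the alternative count they differ only at *g* = 14.
- If the footnote's 4 weeks were counted to Visit 3, the rules would differ only at *g* = 14 (exactly 28 days against more than 28). The footnote refers to the start of the drug, so this reading does not fit its wording.

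**Group B**

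Footnote a applies from 28 days after Visit 1. Reading Visit 1 for Visit 2 in footnote d, the permitted gap is again at most 21 days. A Visit 1 result could therefore be 21 days old at first dose with no retest required.

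**Participants**

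The protocol plans 20 participants, randomized in lots of 4, so Group A has about 20 / 2 = 10. The documents give neither the number of women of child-bearing potential nor the frequency of third-week gaps. The number affected lies between 0 and about 10. The upper end would need everyone in Group A to be a woman of child-bearing potential with a third-week gap, so the true number is probably small.

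**The case against.** The strongest reply is that the protective rule is already in the plan. Every case that triggers the footnote also triggers the text, so a site that follows the text complies with both. A reader might infer that the two rules cannot both be obeyed. The documents do not support that, because the footnote is only looser.

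A reader might also infer that the footnote is defective because it cannot apply within the permitted gap. That does not follow. The gap is loosely worded, and a 4-week trigger can serve as a backstop when scheduling overruns it. Group B's footnote has the same feature. The fault in Group A is the disagreement with the text, not the footnote's silence while the schedule is kept.

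The exposure is also narrow. Acceptable contraception is required, a pregnancy test is done at Visit 2, and the Optional Visit before the SGLT2i segment lists a urine test as needed (though it may be held by phone). Gaps arise only when scheduling is difficult, so the seven disputed days out of 22 (0 to 21) are not a probability.

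All of this stands and limits the weight. It does not remove the mismatch: staff who work from the schedule table at a gap of 15 to 21 days would omit a test that the text requires before drug exposure.

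**Conclusion.** The inconsistency is real and minor. For Group A the text requires the home test from a 15-day gap and the table from 28 days, and they disagree at the third-week gaps that footnote e permits. The practical difference is a pregnancy test up to 7 days older at first dose, in few participants. This rests on reading the permitted gap at its 3-week end and on counting the footnote's 4 weeks to the start of the drug, which is what its wording says.

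The documents do not support a larger conclusion. They do not leave women untested before exposure, since Visit 2 includes a test. The primary outcome, power, randomization and planned analyses are unaffected.

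**What to change.** Use one trigger on one clock in the On-site Visit text and in footnote a of the Group A schedule: a home test with photographic proof of a negative result if more than 14 days pass from the Visit 2 pregnancy test to the first dapagliflozin dose. This keeps the text's present threshold. It also ends the clock at the first dose. If Visit 3 is rescheduled on the morning for glucose or BOHB, the present text condition could become true after dosing has begun, when a pre-dose test is no longer possible.

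Apply the same 14-day limit in Group B's footnote a, counted from the Visit 1 test, so that both groups follow one standard for the same drug. The schedule lists the Visit 1 test as needed, so the wording should make clear that women of child-bearing potential have it. In Group B's footnote d, correct the start of the gap from Visit 2 to Visit 1.

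The cost is one sentence, two footnotes and a one-word correction, plus a few home tests. In Group A the fix adds none beyond what the text already asks for. In Group B it adds at most one for each woman of child-bearing potential with a gap over 14 days.
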